7.2.1.3. International Hidradenitis Suppurativa Severity Score System

The IHS4 ([Zouboulis et al 2017](#)) is a composite, dynamic score, and validated tool, used to determine HS severity. It employs a weighted scale using the number of inflammatory nodules, the number of abscesses, and the number of draining tunnels (eg, fistulas or sinuses), with respective weight factors of 1, 2, and 4. For example, IHS4 score equals the number of inflammatory nodules (multiplied by 1) plus the number of abscesses (multiplied by 2) plus the number of draining tunnels (multiplied by 4).

[REDACTED]

7.2.2. Hurley Stages of Hidradenitis Suppurativa

The Hurley classification is a static score and was originally designed for selection of the appropriate treatment modality in a certain body location (Zouboulis et al 2017): medical therapy for Stage I, local surgery for Stage II, and wide surgical excision for Stage III (see Table 2). Participants who have been diagnosed with HS, Hurley Stage I or II, as per inclusion criterion, will be enrolled into the study. The investigator (or designee) will determine the Global Hurley Stage in each affected anatomical region at the designated study visits. For each participant, an overall Hurley Stage will be derived as the stage of the worst involved anatomical region. The number and proportion of participants in each Hurley Stage will be summarized at baseline and each postbaseline visit.

Table 2: Hurley Stages of Hidradenitis Suppurativa

Hurley Stage	Description
I	Abscess formation, single or multiple, without sinus tracts and cicatrization/scarring.
II	One or more widely separated recurrent abscesses with tract formation and cicatrization/scarring.
III	Multiple interconnected tracts and abscesses across the entire area, with diffuse or near diffuse involvement.

7.2.3. Body Surface Area

Total %BSA affected by HS will be used to determine the number of tubes of study drug dispensed at each visit. Total %BSA affected will be estimated at each visit as outlined in the Protocol. The BSA assessment will be approximated to the nearest 0.1% using the Palmar Method as a guide, with the palm plus 5 digits, with fingers tucked together and thumb tucked to the side (handprint), considered as 1% BSA and the thumb as 0.1% BSA.

7.2.4. Patient-Reported Outcomes

Patient-reported outcomes will be assessed at designated visits as outlined in the Protocol.

For those PROs scheduled to be completed at study visits, on Day 1, the participant will complete their PRO after eligibility is met. For subsequent visits after randomization, questionnaires will be completed by the participant before site personnel perform any clinical assessments to prevent participant bias in their response.

7.2.4.1. Skin Pain Numerical Rating Scale

Participants will be instructed to complete and record the Skin Pain NRS in a diary each evening, beginning on the day of screening through Week 32 or treatment discontinuation, whichever comes first. The participants will rate the severity of their pain associated with HS (ie, burning,

tearing, pulling, stabbing, etc) by selecting a number from 0 (no pain) to 10 (worst imaginable pain) that best describes their worst level of pain in the past 24 hours.

The Skin Pain NRS score for baseline will be determined by averaging the 7 daily NRS scores before Day 1 (ie, Days -7 to -1) for all by-visit summaries. The by-visit Skin Pain NRS score for postbaseline visits will be determined by averaging the 7 daily NRS scores before the visit day. If 4 or more daily scores are missing (out of the 7), the Skin Pain NRS score at the visit will be set to missing. For all the daily pain-related analyses, baseline will be defined as the last available daily pain NRS score during the last week prior to Day 1 (ie, Days -7 to -1).

7.2.4.2. Itch Numerical Rating Scale

The participant will be instructed to complete and record the Itch NRS in a diary each evening beginning on the day of screening through Week 32 or treatment discontinuation, whichever comes first. The participant will rate the severity of their itch associated with HS by selecting a number from 0 (no itch) to 10 (worst imaginable itch) that best describes the worst level of itching in the past 24 hours.

The Itch NRS score for baseline will be determined by averaging the 7 daily NRS scores before Day 1 (ie, Days -7 to -1) for all by-visit summaries. The by-visit Itch NRS score for postbaseline visits will be determined by averaging the 7 daily NRS scores before the visit day. If 4 or more daily scores are missing (out of the 7), the Itch NRS score at the visit will be set to missing. For all the daily itch-related analyses, baseline will be defined as the last available daily Itch NRS score during the last week prior to Day 1 (ie, Days -7 to -1).

the *Journal of the American Statistical Association* (1980, 75, 311-322) and the *Journal of the Royal Statistical Society, Series B* (1981, 43, 1-37). The latter paper is the most comprehensive treatment of the topic, and it is the source of the following summary. The reader is referred to that paper for a detailed treatment of the topic.

7.3. Analysis of the Primary Efficacy Parameter

7.3.1. Primary Efficacy Analysis

The primary analysis will be based on the ITT population. The summary of primary endpoint analysis is provided in [Table 3](#).

Table 3: Summary of Primary Analysis

Parameter	Definition
Treatment effect	Ruxolitinib 1.5% cream compared with vehicle cream
Population	ITT population
Variable	Change from baseline in AN count at Week 16
Population-level summary	Mean change from baseline in AN count at Week 16

Note: All randomized participants, including those with missing Week 16 data, and those who discontinue study treatment at any time before the timepoint of interest, or discontinue from the study for any reason, will be included for the primary analysis. No rescue therapy or treatment switch is allowed in this study.

The primary efficacy analysis will compare ruxolitinib 1.5% cream versus vehicle cream in the mean change from baseline in AN count using an MMRM. The MMRM will include the fixed effect of the treatment group (ruxolitinib 1.5% and vehicle cream), stratification factor (AN count \geq 3 to 4 or AN count \geq 5 to 10 at baseline), visit, and visit by treatment interaction. The variance-covariance matrix of the within-participant errors in MMRM will be modeled as unstructured.

The primary alternative hypothesis (superiority of active ruxolitinib 1.5% cream group compared with vehicle cream) will be tested at a 2-sided $\alpha = 0.1$ level using the least square mean estimate of the change from baseline in AN count at Week 16 from the aforementioned MMRM specified.

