## 10. STATISTICS

### 10.1. Sample Size Determination

Approximately 60 participants will be randomized 1:1 to ruxolitinib cream 1.5% BID or vehicle BID. The sample size was not calculated based on statistical power calculations, but for demonstration of preliminary findings of clinical response. It is anticipated that a sample size of approximately 60 participants will permit sufficient data to be generated to assess whether ruxolitinib cream warrants further investigation in HS. Also, the sample size is considered sufficient to provide enough data for an initial evaluation of the safety profile.

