**Table 11: Summary of Primary Analysis**

Parameter	Definition
Treatment effect	Ruxolitinib 1.5% cream compared with vehicle cream
Population	ITT Population
Variable	Change from baseline in AN count at Week 16
Population-level summary	Mean Change from baseline in AN count at Week 16

Note: All randomized participants, including those with missing Week 16 data, and those who discontinue study treatment at any time before the timepoint of interest, or discontinue from the study for any reason, will be included for the primary analysis. No rescue therapy or treatment switch is allowed in this study.

The primary efficacy analysis will compare ruxolitinib 1.5% cream versus vehicle cream in the mean change from baseline in AN count using a MMRM. The MMRM will include the fixed effect of treatment group (ruxolitinib 1.5% and vehicle cream), stratification factor (AN count  $\geq$  3 to 4 or AN count  $\geq$  5 to 10 at baseline), visit, and visit by treatment interaction. The variance-covariance matrix of the within-participant errors in MMRM will be modeled as unstructured.

The primary alternative hypothesis (superiority of active ruxolitinib 1.5% cream BID group compared with vehicle) will be tested at a 2 sided  $\alpha = 0.1$  level using the least square mean estimate of the change from baseline in AN count at Week 16 from the MMRM specified above. Subgroup analysis by baseline characteristics will be performed.

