#### **10.4.2. Secondary Analysis**

All secondary and [REDACTED] efficacy variables will be summarized using descriptive statistics based on the ITT population. For categorical measurements, summary statistics will include sample size, frequency, and percentages. For continuous measurements, summary statistics will include sample size, mean, median, standard deviation, standard error of the mean, minimum, and maximum. Summary statistics for continuous measures will be provided for baseline, the actual measurements at each visit, and the change and percentage change from baseline at each visit, if applicable. The Skin Pain NRS score for each visit will be determined by averaging the 7 daily Skin Pain NRS scores before the corresponding visit day. If 4 or more daily scores are missing (out of the 7), the Skin Pain NRS score at the visit will be set to missing. The Itch NRS score for each visit will be determined using a similar approach.

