6.1.2. Baseline Disease Characteristics

For the ITT population, the baseline disease characteristics will be summarized and analyzed by treatment group and will include, but not be limited to the following:

- Disease duration (months)
- Prior surgical treatment for HS (yes [incision and drainage, deroofing, or other]/no)
- Prior therapy received for HS
- HS family history (yes/no)
- Selected comorbidities
- Number of anatomical areas with HS
- Days since onset of current episode of HS flare/activity
- Number of HS flares since diagnosis
- Hurley stage
- AN count category (≥ 3 to 4 or ≥ 5 to 10)
- AN count
- Inflammatory nodule count
- Abscess count
- Nondraining tunnel count
- Draining tunnel count
- Skin Pain NRS score
- Itch NRS score
- Total BSA involvement

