7.2.1.1. Abscess and Inflammatory Nodule Counts

The AN counts will be recorded at all visits. The AN results will be used to calculate change in AN count relative to baseline, as well as AN50, AN75, AN90, and AN100, which are defined as, at least, a 50%, 75%, 90%, and 100% decrease, respectively, in AN count relative to baseline.

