7.4.1. Continuous Efficacy Endpoints

The summary and analysis of statistics for the following continuous measurements, including change from baseline, will be presented for each treatment group:

- Total AN count in anatomical areas with pre-existing AN at Week 16
- By-visit Skin Pain NRS score at Week 16
- By-visit Itch NRS score at Week 16
- IHS4 score at Week 16

[figure not shown]
The summary statistics include sample size, mean, median, standard deviation, minimum, maximum, first quartile, third quartile, and 95% confidence interval. A similar MMRM, as specified in the primary efficacy analysis, may be fit for the comparison between ruxolitinib 1.5% cream and vehicle cream at Week 16.

For the endpoint change from baseline in total AN count in anatomical areas with pre-existing AN (ie, not including new AN identified after baseline), only the anatomical areas with an AN count > 0 will be considered for each participant. At baseline, the anatomical areas with abscesses and/or inflammatory nodules will be identified and AN counts in these areas will be summed. At each postbaseline visit, the sum of AN counts in only the pre-existing areas (that were identified at baseline) will be used to calculate the change relative to baseline.

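### The primary MMRM adjusts for baseline AN count only as 3–4 versus 5–10; prespecifying the exact count as well is a near-costless change that may recover some precision, by an amount the documents cannot settle.

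*SAP*

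**What the plan says.** The primary model is the same in both documents. SAP 7.3.1: "The MMRM will include the fixed effect of the treatment group (ruxolitinib 1.5% and vehicle cream), stratification factor". Protocol 10.4.1: "The MMRM will include the fixed effect of treatment group (ruxolitinib 1.5% and vehicle cream), stratification factor". In each, the stratification factor has two levels, baseline AN count 3 to 4 or 5 to 10. The remaining terms are visit and visit by treatment, with an unstructured covariance matrix. The test is two-sided at 0.1 on the Week 16 least-squares means.

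The exact count is available. SAP 7.2.1.1: "The AN results will be used to calculate change in AN count relative to baseline". SAP 6.1.2 lists "AN count category" and, as a separate baseline item, the AN count itself. No visible section adds the exact count to the primary model. The only departure from the protocol logged in SAP 11.1 is an added secondary endpoint.

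On size, Protocol 10.1: "The sample size was not calculated based on statistical power calculations, but for demonstration of preliminary findings of clinical response". About 60 participants are randomized 1:1. Neither document gives an effect size, an SD or a power.

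For secondary endpoints, Protocol 10.4.2 says "efficacy variables will be summarized using descriptive statistics based on the ITT population". SAP 7.4.1 adds an option: "A similar MMRM, as specified in the primary efficacy analysis, may be fit for the comparison between ruxolitinib 1.5% cream and vehicle cream". Baselines for the diary scores are defined, for example in SAP 7.2.4.1: "The Skin Pain NRS score for baseline will be determined by averaging the 7 daily NRS scores before Day 1".

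**The concern.** Eligibility fixes the baseline count at 3 to 10, so the upper stratum treats a participant with 5 lesions like one with 10. If change depends on baseline within a stratum, two things follow. Part of the residual variance is explainable but left unexplained, and chance imbalance in baseline count within strata adds noise to the treatment difference. A single covariate that is already in the database would remove both.

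The stake is precision. The sample size was not set by power and the trial is meant to show whether the cream is worth pursuing in HS, so any precision available without recruiting more participants is useful. Randomization protects the planned comparison either way.

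**Working it through.** **No figure to reproduce.** The plan states no power or precision for the primary comparison.

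**Inputs from the documents.** About 60 participants, 1:1; two-sided alpha 0.1; baseline AN an integer from 3 to 10; strata 3–4 and 5–10.

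**Assumed inputs.** Four baseline distributions; slope of Week 16 change on baseline b = -0.3, -0.5 or -0.7; residual SD given baseline 2.5 or 3.

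**Step 1: how much the stratum captures.** Vw is the within-stratum variance and V the total. Share captured = 1 - Vw/V. SD of the between-arm imbalance at 30 per arm = sqrt(2·Vw/30).

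| Assumed distribution on 3–10 | Vw | V | Captured | Imbalance SD (lesions) |
|---|---|---|---|---|
| Uniform | 2.25 | 5.25 | 57% | 0.39 |
| Each count 0.75 times as likely as the one below | 1.41 | 4.09 | 65% | 0.31 |
| Each count 0.6 times as likely | 0.82 | 2.64 | 69% | 0.23 |
| Each count 1.25 times as likely | 2.39 | 4.50 | 47% | 0.40 |

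The stratum captures 47–69% and leaves 31–53%.

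**Step 2: closed-form gain.** With the stratum only, the residual variance is b²·Vw + SD². With the exact count added it is SD². The gross reduction is g = b²·Vw/(b²·Vw + SD²). One extra parameter costs about 1/56 (60 minus 4 mean parameters), so the net reduction is 1 - (1 - g)(1 + 1/56).

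- Least favourable cell (0.6 distribution, b = -0.3, SD 3): g = 0.0735/9.0735 = 0.8%; net 1.0% **higher** variance.
- Middle cell (uniform, b = -0.5, SD 3): g = 0.5625/9.5625 = 5.9%; net 4.2% lower.
- Most favourable cell (1.25 distribution, b = -0.7, SD 2.5): g = 1.172/7.422 = 15.8%; net 14.3% lower.

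Over the 24 cells (4 distributions × 3 slopes × 2 SDs):

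| Slope | Net change in variance of the treatment difference |
|---|---|
| -0.3 | 1.0% higher to 1.6% lower |
| -0.5 | 0.5% to 7.1% lower |
| -0.7 | 2.5% to 14.3% lower |

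The median is 3.1% lower, and 4 of the 24 cells reach 9%. Outside this grid, a slope of zero gives g = 0, and the cost is the full 1/56, or 1.8% higher variance.

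**Step 3: what the median means.** The interval narrows by 1 - sqrt(0.969) = 1.6%. Effective size is 60/0.969 = 61.9, about 2 participants. For power, take an assumed 70% start: (1.645 + 0.524)/sqrt(0.969) - 1.645 = 0.559, which is 71%.

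**Step 4: simulation of the planned model.** The five-visit unstructured MMRM was simulated with overdispersed counts in 48 scenarios: the four distributions, two pairs of Week 16 multipliers of baseline (vehicle/active 0.65/0.45 and 0.5/0.3), shrinkage s of baseline toward its mean of 0, 25% and 50%, with and without dropout; 1,500 replicates each. Adding one common baseline slope lowered the variance by 1.5–20%, median 9%. By shrinkage 0, 25% and 50% the ranges were 1.5–10%, 4–14% and 7–20%. A baseline-by-visit term never differed from the common slope by more than 1.1 percentage points. Monte Carlo error is about 1–2 points.

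The implied arm-averaged slope in these scenarios is (mean multiplier)(1 - s) - 1:

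- 0.65/0.45: -0.45, -0.59, -0.725
- 0.5/0.3: -0.60, -0.70, -0.80

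No scenario includes -0.3, and half are at -0.7 or beyond. The 9% is a median over steep slopes, not an expected gain.

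**Step 5: separate check.** A Week 16-only simulation with complete data gave a standard error 1–11% lower when the slope of change was -0.75 to -0.5, and about no change (0.8% higher to 1.1% lower) when it was -0.25 to 0. The direction and order of size agree with Steps 2 and 4.

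**The case against.** The strongest reply is that one valid prespecified model would be swapped for another on the strength of an assumed slope. The planned model adjusts for the randomization stratum, agrees exactly between protocol and SAP, and on the figures above already captures about half to two thirds of the baseline variance. That stands, and it limits the point to an improvement.

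Four stronger readings are tempting, and the documents support none of them.

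- **That the omission biases the result or inflates type I error.** Nothing in either document points that way; allocation is randomized and the stratum is in the model.
- **That the count's floor at zero proves a slope within strata.** It does not. If Week 16 counts tracked baseline one for one, the slope of change would be zero. Entry with at least 3 lesions at both screening and baseline makes regression to the mean plausible, but that remains an assumption.
- **That the gain is about 9%, worth about 6 participants and a rise from 70% to about 73% power.** This takes the median of the steep-slope simulations as the expected value. The closed form, which includes slope -0.3, has a median near 3%.
- **That the Skin Pain and Itch analyses are wrong because their own baselines are left out.** SAP 7.4.1 says only that a model like the primary one may be fitted. It neither requires nor excludes the endpoint's own baseline. This is a wording gap in an optional analysis.

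**Conclusion.** The point holds as a cheap efficiency improvement to a valid analysis. The primary model uses baseline AN count in two categories when the exact count is in hand, and under the assumed distributions 31–53% of the baseline variance stays unadjusted.

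The size is unknown, because the documents give no SD, slope or baseline distribution. A fair statement is from about 1% higher to 14% lower variance, centred near 3%, with up to 20% lower only if change depends steeply on baseline. The direction rests on an assumed negative slope within strata. The payoff is lopsided: at worst a loss of 1–2% of variance, at best several participants' worth of information. A reader should not infer that the primary result would be unreliable without the change.

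**What to change.** In SAP 7.3.1, add baseline AN count as a continuous covariate with one common slope and keep the stratification factor. A baseline-by-visit term is optional and made no material difference in simulation. Record the departure from the Protocol 10.4.1 model in SAP 11.1.

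Timing matters. The change must be made before the primary database lock, because SAP 10 has the sponsor unblinded after it. A covariate chosen after that point would not be credible as part of the primary analysis.

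Optional clarification in SAP 7.4.1: if the optional MMRM is fitted, include each endpoint's own baseline (Skin Pain NRS, Itch NRS, IHS4, and AN count in pre-existing areas).

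Cost: one phrase in 7.3.1, one entry in 11.1 and, if wanted, one sentence in 7.4.1. The primary model gains one parameter. No new data are needed and no participant is lost, because the change score already requires the baseline count. The gain may be nil, or a loss of about 1% (1.8% at a slope of exactly zero).

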7.3.2. Subgroup Analyses for Primary Endpoint

Subgroups will be formed based on the following participant characteristics and baseline variables for those participants whose data are available:

- Baseline AN count: ≥ 3 to 4 or ≥ 5 to 10
- Age group: 18 to 29 years or ≥ 30 years

The primary efficacy endpoint will be summarized and analyzed using descriptive statistics based on the ITT population for the aforementioned subgroups.

7.4. Analysis of the Secondary Efficacy Parameters

All secondary efficacy analyses will be conducted for the ITT population.

7.4.1. Continuous Efficacy Endpoints

The summary and analysis of statistics for the following continuous measurements, including change from baseline, will be presented for each treatment group:

- Total AN count in anatomical areas with pre-existing AN at Week 16
- By-visit Skin Pain NRS score at Week 16
- By-visit Itch NRS score at Week 16
- IHS4 score at Week 16

[figure not shown]
The summary statistics include sample size, mean, median, standard deviation, minimum, maximum, first quartile, third quartile, and 95% confidence interval. A similar MMRM, as specified in the primary efficacy analysis, may be fit for the comparison between ruxolitinib 1.5% cream and vehicle cream at Week 16.

For the endpoint change from baseline in total AN count in anatomical areas with pre-existing AN (ie, not including new AN identified after baseline), only the anatomical areas with an AN count > 0 will be considered for each participant. At baseline, the anatomical areas with abscesses and/or inflammatory nodules will be identified and AN counts in these areas will be summed. At each postbaseline visit, the sum of AN counts in only the pre-existing areas (that were identified at baseline) will be used to calculate the change relative to baseline.

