## 6. STUDY TREATMENT

### 6.1. Study Treatment(s) Administered

Ruxolitinib 1.5% cream or matching vehicle cream will be applied as a thin film BID, with applications approximately 8 hours apart in the morning and in the evening at least 1 hour before bedtime.

At the baseline visit, an estimate of the %BSA ( $\leq 20\%$ ) affected by HS (total AN count 3 to  $\leq 10$ ) to be treated (excluding scalp) will be used by the IRT system to calculate the number of tubes of study drug to be dispensed. The participant will apply a thin film of study drug in front of site staff at the baseline/Day 1 visit by applying small amounts of study drug on each nodule and the surrounding area of the nodule ( $\approx 1$  cm). All areas identified at baseline should continue to be treated through the end of the DBVC period (Week 16) unless the participant meets criteria for stopping study drug. If there are new AN to be treated, after consultation with the investigator, study drug should be applied to these AN in addition to the areas treated at baseline (maximum total affected areas  $\leq 20\%$  BSA), and the percentage of BSA to be treated will be recalculated and increased. This new estimate will be entered into the IRT system to calculate the number of tubes of study drug to be dispensed. Participants whose additional new areas to be treated in addition to the areas identified at the baseline visit exceed 20% BSA should be discontinued from study treatment and ET assessment should be completed.

At Week 16 and starting the OLE period, participants will be evaluated by the investigator to confirm whether they:

- require continuation of therapy due to AN count  $\geq 1$  and/or the presence of pain (Skin Pain NRS  $\geq 1$ ) or,
- can begin an observation/no treatment cycle due to AN count = 0 and no pain [Skin Pain NRS of 0]).

At Week 16, the IRT system will dispense a prespecified number of tubes according to the assessment of total BSA to be treated.

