2.2. Study Objectives and Endpoints

[Table 1](#) presents the objectives and endpoints.

Table 1: Objectives and Endpoints

Objectives	Endpoints
Primary	
To establish the efficacy of ruxolitinib 1.5% cream BID in participants with HS.	Change from baseline in AN count at Week 16.
Secondary	
To further evaluate the treatment effect of ruxolitinib 1.5% cream BID in participants with HS.	
Change from baseline to Week 16 in total AN count in anatomical areas with pre-existing AN at baseline. Note: Pre-existing AN at baseline are defined as abscesses and/or inflammatory nodules present at baseline.Proportion of participants achieving AN50, AN75, AN90, and AN100 (at least 50%, 75%, 90%, and 100% reduction, respectively, in AN count relative to baseline) at Week 16.Change from baseline in the Skin Pain NRS score at Week 16.Change from baseline in the Itch NRS score at Week 16.Proportion of participants who achieve HiSCR at Week 16. Note: HiSCR is defined as at least 50% reduction in AN count with no increase in either abscess or draining fistula counts, relative to baseline.Change from baseline in the IHS4 score at Week 16.Note: IHS4 score is calculated by the number of inflammatory nodules (multiplied by 1) plus the number of abscesses (multiplied by 2) plus the number of draining tunnels (multiplied by 4).
To evaluate the safety and tolerability of ruxolitinib 1.5% cream BID in participants with HS.	The type, frequency, and severity of AEs, and changes in vital signs and hematology and serum chemistry parameters.

Table 1: Objectives and Endpoints (Continued)

[figure not shown]

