7.2. Efficacy Measures

7.2.1. Lesion Counts

The HS lesion counts will be assessed at each study visit by the investigator and used for calculation of efficacy parameters as follows: AN counts, HiSCR, IHS4, and flare incidence.

Lesion count and assessment will be recorded in the lesion count worksheet; the assessment of anatomical regions includes, but is not limited to the left and right axilla and the left and right inguinocrural fold or inframammary areas.

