11.1. Changes to Protocol-Defined Analyses

1. Section 2.2, Study Objectives and Endpoints

Description of change: Added the secondary endpoint, "Change from baseline to Week 16 in total AN count in anatomical areas with pre-existing AN at baseline."

Rationale for change: To further evaluate the treatment effect of ruxolitinib 1.5% cream BID in participants with HS.

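### Does the aside in SAP 7.4.1 about new AN contradict the formula for AN change in areas affected at baseline?

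*SAP*

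**What the plan says.** The protocol's endpoint table does not list this endpoint. The SAP adds it, and section 11.1 declares the addition under the name "Change from baseline to Week 16 in total AN count in anatomical areas with pre-existing AN at baseline". A note in SAP Table 1 (section 2.2) adds: "Pre-existing AN at baseline are defined as abscesses and/or inflammatory nodules present at baseline".

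Section 7.4.1 gives the derivation. After naming the endpoint it inserts the aside "ie, not including new AN identified after baseline". It then states the rule in two steps:

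- First step, for the starting value: "the anatomical areas with abscesses and/or inflammatory nodules will be identified and AN counts in these areas will be summed".
- Second step, for all later visits: "the sum of AN counts in only the pre-existing areas (that were identified at baseline) will be used to calculate the change".

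Two other places bear on the point. SAP 7.2.1 says "Lesion count and assessment will be recorded in the lesion count worksheet" and describes assessment by anatomical region. Protocol 6.1 foresees new lesions during the double-blind period: "If there are new AN to be treated, after consultation with the investigator, study drug should be applied to these AN".

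**The concern.** The aside opens with the abbreviation that signals a restatement, and it puts no limit by area on the new AN it sets aside. The formula has no step that removes a new AN when it appears inside an area already affected at baseline. Taken at face value, the two describe different quantities. The aside would give the fate of the lesions present at baseline. The formula gives a net count within the baseline areas, where resolved and new lesions offset each other.

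Interpretation is what would be at stake. A report that carried the aside forward could present the result as free of new lesions when it is not. Because the endpoint was introduced in the SAP, section 7.4.1 is the only place in the documents where a reader finds its derivation. New AN are expected, and nothing in the protocol says they arise only in areas that were clear at baseline.

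**Working it through.** The plan gives no figure to reproduce here: the sample size of about 60 is not power-based, and the point concerns a definition. The check is therefore algebraic, followed by a comparison of the texts.

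**Notation, per participant at one visit**

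- B = AN at baseline. By construction all of them lie in baseline-affected areas.
- r = baseline AN that have resolved.
- k = new AN in baseline-affected areas.
- m = new AN in areas clear at baseline.

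**Change from baseline under each definition**

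- Primary endpoint, all areas: (B − r + k + m) − B = k + m − r.
- Formula in SAP 7.4.1: (B − r + k) − B = k − r.
- Aside, read as removing every new AN: (B − r) − B = −r.

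The formula differs from the primary endpoint by m alone. It differs from the literal aside by (k − r) − (−r) = k. Between arms, the two descriptions differ by mean k on active minus mean k on vehicle, which is zero if new AN in baseline areas are equally common in both arms. A made-up case confirms the identity: B = 3, r = 3, k = 1 gives 1 − 3 = −2 by the formula and −3 by the literal aside, a gap of 1. Neither document gives a value for k, so no realistic size can be attached.

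**Which reading the text supports**

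1. *Position.* The aside directly follows the words on pre-existing AN. Attached there, it says that an area qualifies through lesions present at baseline and not through lesions found later. That agrees with the formula.
2. *The Table 1 note.* It defines pre-existing AN by presence at baseline. It identifies areas and does not restrict what is counted in them later. The aside can be read as the same definition in negative form.
3. *The formula.* Both steps are explicit and can be programmed as they stand. The second is confined to areas and says nothing about sorting lesions into old and new.
4. *Names and titles.* The endpoint name in Table 1 and section 11.1, and the planned table and figures in SAP Appendix A (Table 2.1.2, Figures 4.1.2.1 to 4.1.2.3), all refer to areas.
5. *Data.* The visible text describes counts by region on a worksheet and no marking of single lesions. The worksheet itself is not in the documents and some text is redacted, so this is supporting evidence only.

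Only the literal reading of the aside points to a lesion-level endpoint. Everything else points to the area-level count.

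**The case for a change.** The strongest case for a change is that a definition should not contain words that are false on their plain meaning. The aside does not mention areas, and a reader who combines it with the Table 1 note could fairly expect a lesion-level result. HS lesions recur, so new AN in an already affected area are not remote. If k differed between arms, the two descriptions could support different statements about the treatment effect. The correction would cost one sentence.

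Part of this stands. The aside is loosely worded, the algebra is right, and the formula does count new AN inside baseline areas. What does not stand is the claim of a flat contradiction, because the nearer attachment of the aside removes it. Nor is there a route to a wrong result: no section plans to report the endpoint as excluding new lesions, and the planned titles describe it correctly. The endpoint is also secondary, is summarized descriptively, and has only an optional model-based comparison.

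**Conclusion.** No change to the plan follows. The aside is ambiguous, but the same paragraph settles the calculation, and the endpoint name and output titles settle the description. Rewording it would change no calculated value, no data collection, no program and no test, and the primary endpoint is unaffected. The gap of k arises only under the literal reading, and its size in this trial is unknown.

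This rests on two assumptions: that the analysts program the two explicit steps in SAP 7.4.1, and that the report keeps the area-level label already planned. On that basis the result is the net AN change within baseline-affected areas and should be read as that.
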